3.5.2.3 Other Outcome Variables

Responses to the Resource Utilization Form (RUF) will be summarized appropriately to explore the impact of treatment on health care resources.

3.6 Trial Procedures

The duration of this trial from first subject enrolled to last subject completed is estimated to be approximately 57 months, of which approximately 51 months are allotted for rollover of subjects from prior double-blind phase 3 brexpiprazole MDD trials. Individual participation for subjects who complete the trial without early withdrawal will be approximately 30 weeks (26 weeks of treatment and 30-day follow-up). Trial assessment time points are summarized in [Table 3.6-1](#).

Table 3.6-1 Schedule of Assessments

Assessment	Screening/ Baseline ^a	Open-Label Treatment Phase Visit Week (± 2 days)							Follow-up ^c 30 (+2) days
		1	2	4	8	14	20	26/ET ^b	
ENTRANCE CRITERIA									
Informed consent ^d	X								
Inclusion/exclusion criteria	X								
Medical history	X ^e								
EFFICACY									
CGI-S	X	X	X	X	X	X	X	X	
CGI-I ^f	X					X		X	
SDS	X					X		X	
IDS-SR	X					X		X	
SAFETY									
Physical examination	X							X	
Waist circumference	X					X		X	
Vital signs ^g	X	X	X	X	X	X	X	X	
12-lead ECG ^h	X					X		X	
Clinical laboratory tests ⁱ	X ^j					X ^k		X ^k	
HbA1c	X ^j					X ^k		X ^k	
Drug screen/blood alcohol ^l	X	X		X	X	X		X	
Urine pregnancy test (WOCBP only) ^m	X	X	X	X	X	X	X	X	
SAS	X	X	X	X	X	X	X	X	
AIMS	X					X		X	
BARS	X	X	X	X	X	X	X	X	
C-SSRS ⁿ	X	X	X	X	X	X	X	X	
MSFQ	X							X	
Adverse events	X ^o	X	X	X	X	X	X	X	X

Assessment	Screening/ Baseline ^a	Open-Label Treatment Phase Visit Week (\pm 2 days)							Follow-up ^c 30 (+2) days
		1	2	4	8	14	20	26/ET ^b	
Concomitant medications ^p	X	X	X	X	X	X	X	X	X
OTHER									
Dose adjustments ^q		X	X	X	X	X	X		
RUF ^r	X							X	
Register visit in IVRS/IWRS ^s	X	X	X	X	X	X	X	X	
IMP dispensing	X	X	X	X	X	X	X		
IMP accountability		X	X	X	X	X	X	X	

IVRS = interactive voice response system; IWRS = interactive web response system; WOCBP = women of childbearing potential.

^aScreening for Trial 331-10-238 occurs simultaneously with Baseline at the last scheduled visit of the prior double-blind phase 3 trial. All assessments listed under screening need to be performed at Screening/Baseline of Trial 331-10-238; if any of these assessments were conducted at the last scheduled visit of the prior double-blind phase 3 trial, then Screening/Baseline values for those assessments will be derived from that visit and those assessments will not need to be repeated at Screening/Baseline of Trial 331-10-238.

^bIf a subject discontinues prematurely before Week 26, procedures noted for Week 26 must be completed at the early termination (ET) visit. Subjects who have completed 26 weeks or more, will have the Week 26/ET procedures at their next scheduled visit.

^cConsists of telephone contact or clinic visit (investigator's discretion) for evaluation of safety and applies to all subjects (completers and early withdrawals).

^dInformed consent for Trial 331-10-238 will occur at Screening/Baseline and must be obtained before any trial-related procedures specific to the open-label trial are performed.

^eUpdate, if necessary.

^fImprovement should be based on the subject's status at the last scheduled visit of the prior double-blind phase 3 trial.

^gVital signs include body weight, body temperature, systolic blood pressure (SBP), diastolic blood pressure (DBP), and heart rate. Blood pressure and heart rate will be measured in the following order: supine, sitting, and standing after the subject has been in each position for at least 3 minutes. Vital signs scheduled for the same visit as blood samples are to be completed before blood is drawn.

^hStandard 12-lead ECGs will be performed after the subject has been supine and at rest for \geq 5 minutes prior to the ECG. A central ECG service will be utilized to review all ECGs in order to standardize interpretations for the safety analysis. In addition, ECG results will be evaluated at the investigational site to monitor safety during the trial. Subjects will be enrolled in Trial 331-10-238 based on the screening/baseline ECG results from the trial site. If the screening/baseline ECG results from the central reader (ie, the last scheduled visit of the prior double-blind phase 3 trial), when available, indicate a QTcF

≥ 450 msec at screening/baseline, the investigator must contact the medical monitor to discuss the subject's continued participation in the trial. ECGs scheduled for the same visit as blood samples are to be completed before blood is drawn.

ⁱIncludes hematology (including PT, aPTT, and INR), serum chemistry (including prolactin and TSH, with reflex to free thyroxine [T₄] if the result for TSH is abnormal), and urinalysis.

^jSubjects must be fasting for a minimum of 8 hours prior to blood draws for screening/baseline laboratory assessments (ie, the last scheduled visit of the prior double-blind phase 3 trial).

^kClinical laboratory tests should be drawn fasting, if possible, but must be drawn after a minimum 8-hour fast at Week 26/ET. Vital sign and ECG assessments should be completed before any blood samples are collected.

^lA urine drug screen and a blood alcohol test are required at the designated times, but either or both can be conducted at any time during the trial at the discretion of the investigator.

^mAll positive urine pregnancy test results must be confirmed by a serum test. Subjects with a positive serum pregnancy test result at Screening/Baseline must not be enrolled in Trial 331-10-238 and subjects with a positive serum pregnancy test result during the trial must discontinue treatment and be withdrawn from the trial. Pregnancy tests can be performed at any point during the trial if pregnancy is suspected.

ⁿ“Since Last Visit” C-SSRS form.

^oAE recording will begin with the signing of the ICF for Trial 331-10-238.

^pAll prescription and non-prescription medications taken during the trial will be recorded as concomitant medications. Details of prohibited and restricted medications are provided in [Section 4](#).

^qAdjustments to the dose of brexpiprazole or ADT are permitted to optimize efficacy and tolerability as described in [Section 3.2](#). It is recommended that the dose of ADT not be changed while the dose of brexpiprazole is being optimized (ie, no change to ADT up to and including the Week 4 visit). At least 5 days must elapse between dose increases for brexpiprazole and ADT. An interval of at least 5 days between dose adjustments is also recommended for dose decreases; however, the investigator may decrease the dose of brexpiprazole or ADT as needed for tolerability according to the rules described in [Section 3.2.2](#). Subjects must return to the clinic for unscheduled visits if changes to the dose of brexpiprazole or ADT (increases or decreases) are required between scheduled visits. All eligible subjects entering from prior double-blind phase 3 brexpiprazole MDD trials must be able to continue therapy without interruption between the double-blind and open label trials.

^rBaseline RUF is completed at Screening/Baseline for all subjects. The Follow-up RUF (as well as hospitalization questions) is completed at Week 26/ET visit.

^sThe IVRS/IWRS will be accessed at unscheduled visits if new blister cards are dispensed for dose adjustment of brexpiprazole.

3.6.1 Schedule of Assessments

3.6.1.1 Screening/Baseline

Subjects entering Trial 331-10-238 must sign the ICF for the open-label trial before any procedures specific to Trial 331-10-238 can be performed. Subjects will retain the same subject identification (Subject ID) number assigned in the prior double-blind phase 3 trial. The following procedures need to be performed at Screening/Baseline of Trial 331-10-238; if any of these assessments were conducted at the last scheduled visit of the prior double-blind phase 3 trial, then Screening/Baseline values for those assessments will be derived from that visit and those assessments will not need to be repeated at Screening/Baseline of Trial 331-10-238.

- Inclusion/exclusion criteria for Trial 331-10-238 will be reviewed to assure the subject's eligibility.
- Medical history will be updated, if necessary, using information from the prior double-blind phase 3 trial.
- Subjects will submit to a physical examination and assessments of waist circumference, vital signs, and ECG.
- The investigator (or qualified designee) will administer the CGI-S and CGI-I.
- Subjects will complete any Baseline instrument (ie, SDS, IDS-SR, and MSFQ).
- An adequately trained and experienced clinician will administer any EPS scale (ie, SAS, AIMS, and BARS).
- The investigator (or qualified designee) will complete the “Since Last Visit” C-SSRS form.
- Concomitant medications will be reviewed to assure that the subject is not receiving any prohibited medications.
- Subjects will complete the Baseline RUF.
- For subjects entering Trial 331-10-238 after completing the last scheduled visit of the prior double-blind phase 3 trial, a fasting blood sample will be drawn for analysis of any clinical laboratory parameter (ie, the clinical laboratory parameters specified in **Table 3.6.2.1-1**) that was not drawn at the last scheduled visit of the prior double-blind phase 3 trial.
- AE recording will begin with the signing of the ICF for Trial 331-10-238.
- Trial personnel will call the interactive voice response system (IVRS) or access the interactive web response system (IWRS) to register the visit and to obtain blister card and ADT bottle number assignments. The assigned open-label brexpiprazole and ADT will be dispensed. Treatment will begin with brexpiprazole 0.5 mg/day for 1 week. The ADT will be the same as the one taken during the prior double-blind phase 3 trial. The dose of ADT should not be changed at this time.

3.6.1.2 Week 1

All subjects will attend a visit at Week 1 (\pm 2 days) where the following evaluations will be performed:

- The investigator (or qualified designee) will administer the CGI-S.
- An adequately trained and experienced clinician will administer the SAS and BARS to assess EPS.
- The investigator (or qualified designee) will complete the “Since Last Visit” C-SSRS form.
- Vital sign measurements (body weight, body temperature, blood pressure, and heart rate) will be recorded. Blood pressure and heart rate are to be measured in the following order: supine, sitting, and standing after the subject has been in each position at least 3 minutes. Vital signs are to be completed before any blood is drawn.
- Samples will be obtained for blood alcohol testing.
- Urine will be collected for urine screen(s) for drugs of abuse.
- Women of childbearing potential (WOCBP) will be given a urine pregnancy test. Any positive result must be confirmed by a serum pregnancy test. WOCBP with a positive serum pregnancy test result must discontinue the IMP and be withdrawn from the trial.
- Drug accountability will be performed for brexpiprazole and ADT.
- The dose of brexpiprazole will be increased to 1 mg/day. Subjects unable to tolerate brexpiprazole 1 mg/day may decrease to 0.5 mg/day at any time after the Week 1 visit. It is recommended that the dose of ADT not be changed while the dose of brexpiprazole is being optimized. Trial personnel will call the IVRS or access the IWRS to register the visit, to enter dose details for brexpiprazole and ADT, and to obtain blister card and bottle number assignments. The assigned open-label brexpiprazole and ADT will be dispensed to the subject.
- AEs and concomitant medications will be recorded.

3.6.1.3 Week 2

All subjects will attend a visit at Week 2 (\pm 2 days) where the following evaluations will be performed:

- The investigator (or qualified designee) will administer the CGI-S.
- An adequately trained and experienced clinician will administer the SAS and BARS to assess EPS.
- The investigator (or qualified designee) will complete the “Since Last Visit” C-SSRS form.

- Vital sign measurements (body weight, body temperature, blood pressure, and heart rate) will be recorded. Blood pressure and heart rate are to be measured in the following order: supine, sitting, and standing after the subject has been in each position at least 3 minutes.
- WOCBP will be given a urine pregnancy test. Any positive result must be confirmed by a serum pregnancy test. WOCBP with a positive serum pregnancy test result must discontinue the IMP and be withdrawn from the trial.
- Drug accountability will be performed for brexpiprazole and ADT.
- The investigator will adjust the dose of brexpiprazole as necessary as described in [Section 3.2](#) to achieve optimal efficacy and tolerability. It is recommended that the dose of ADT not be changed while the dose of brexpiprazole is being optimized. Any subject unable to tolerate the minimum dose of brexpiprazole (ie, 0.5 mg/day) must be withdrawn from the trial. Trial personnel will call the IVRS or access the IWRS to register the visit, to enter dose details for brexpiprazole and ADT, and to obtain blister card and bottle number assignments. The assigned open-label brexpiprazole and ADT will be dispensed to the subject.
- AEs and concomitant medications will be recorded.

3.6.1.4 Week 4

All subjects will attend a visit at Week 4 (\pm 2 days) where the following evaluations will be performed:

- The investigator (or qualified designee) will administer the CGI-S.
- An adequately trained and experienced clinician will administer the SAS and BARS to assess EPS.
- The investigator (or qualified designee) will complete the “Since Last Visit” C-SSRS form.
- Vital sign measurements (body weight, body temperature, blood pressure, and heart rate) will be recorded. Blood pressure and heart rate are to be measured in the following order: supine, sitting, and standing after the subject has been in each position at least 3 minutes. Vital signs are to be completed before any blood is drawn.
- Samples will be obtained for blood alcohol testing.
- Urine will be collected for urine screen(s) for drugs of abuse.
- WOCBP will be given a urine pregnancy test. Any positive result must be confirmed by a serum pregnancy test. WOCBP with a positive serum pregnancy test result must discontinue the IMP and be withdrawn from the trial.
- Drug accountability will be performed for brexpiprazole and ADT.
- The investigator will adjust the dose of brexpiprazole as necessary as described in [Section 3.2](#) to achieve optimal efficacy and tolerability. If necessary, the dose of

ADT can be changed after the Week 4 visit, but not at the same visit as a change to the dose of brexpiprazole (see [Section 3.2.2.2](#)). Any subject unable to tolerate the minimum dose of brexpiprazole (ie, 0.5 mg/day) must be withdrawn from the trial. Trial personnel will call the IVRS or access the IWRS to register the visit, to enter dose details for brexpiprazole and ADT, and to obtain blister card and bottle number assignments. The assigned open-label brexpiprazole and ADT will be dispensed to the subject.

- AEs and concomitant medications will be recorded.

3.6.1.5 Week 8

All subjects will attend a visit at Week 8 (\pm 2 days) where the following evaluations will be performed:

- The investigator (or qualified designee) will administer the CGI-S.
- An adequately trained and experienced clinician will administer the SAS and BARS to assess EPS.
- The investigator (or qualified designee) will complete the “Since Last Visit” C-SSRS form.
- Vital sign measurements (body weight, body temperature, blood pressure, and heart rate) will be recorded. Blood pressure and heart rate are to be measured in the following order: supine, sitting, and standing after the subject has been in each position at least 3 minutes. Vital signs are to be completed before any blood is drawn.
- Samples will be obtained for blood alcohol testing.
- Urine will be collected for urine screen(s) for drugs of abuse.
- WOCBP will be given a urine pregnancy test. Any positive result must be confirmed by a serum pregnancy test. WOCBP with a positive serum pregnancy test result must discontinue the IMP and be withdrawn from the trial.
- Drug accountability will be performed for brexpiprazole and ADT.
- The investigator will adjust the dose of brexpiprazole as necessary within the range of 0.5 to 3 mg daily as described in [Section 3.2](#). If necessary, the dose of ADT can also be adjusted (see [Section 3.2.2.2](#)). Trial personnel will call the IVRS or access the IWRS to register the visit, to enter dose details for brexpiprazole and ADT, and to obtain blister card and bottle number assignments. The assigned open-label brexpiprazole and ADT will be dispensed to the subject.
- AEs and concomitant medications will be recorded.

3.6.1.6 Week 14

All subjects will attend a visit at Week 14 (\pm 2 days) where the following evaluations will be performed:

- The investigator (or qualified designee) will administer the CGI-S and CGI-I.
- Waist circumference will be measured.
- An adequately trained and experienced clinician will administer the SAS, AIMS, and BARS to assess EPS.
- The subject will complete the IDS-SR and SDS.
- The investigator (or qualified designee) will complete the “Since Last Visit” C-SSRS form.
- Vital sign measurements (body weight, body temperature, blood pressure, and heart rate) will be recorded. Blood pressure and heart rate are to be measured in the following order: supine, sitting, and standing after the subject has been in each position at least 3 minutes. Vital signs are to be completed before any blood is drawn.
- A standard 12-lead ECG will be performed after the subject has been supine and at rest for at least 5 minutes. The ECG is to be completed before any blood is drawn.
- A fasting blood draw will be collected for clinical laboratory tests (hematology, including PT, aPTT, and INR; and serum chemistry, including prolactin, HbA1c, and TSH, with reflex to free T4 if the result for TSH is abnormal). Vital sign and ECG assessments should be completed before any blood samples are collected.
- Samples will be obtained for blood alcohol testing. Additional blood alcohol testing may be performed at any other time at the discretion of the investigator.
- Urine will be collected for urinalysis and urine screen(s) for drugs of abuse. Additional urine drug screens may be performed at any other time at the discretion of the investigator.
- WOCBP will be given a urine pregnancy test. Any positive result must be confirmed by a serum pregnancy test. WOCBP with a positive serum pregnancy test result must discontinue the IMP and be withdrawn from the trial.
- Drug accountability will be performed for brexpiprazole and ADT.
- The investigator will adjust the dose of brexpiprazole as necessary within the range of 0.5 to 3 mg daily as described in [Section 3.2](#). If necessary, the dose of ADT can also be adjusted (see [Section 3.2.2.2](#)). Trial personnel will call the IVRS or access the IWRS to register the visit, to enter dose details for brexpiprazole and ADT, and to obtain blister card and bottle number assignments. The assigned open-label brexpiprazole and ADT will be dispensed to the subject.
- AEs and concomitant medications will be recorded.

3.6.1.7 Week 20

All subjects will attend a visit at Week 20 (\pm 2 days) where the following evaluations will be performed:

- The investigator (or qualified designee) will administer the CGI-S.
- An adequately trained and experienced clinician will administer the SAS and BARS to assess EPS.
- The investigator (or qualified designee) will complete the “Since Last Visit” C-SSRS form.
- Vital sign measurements (body weight, body temperature, blood pressure, and heart rate) will be recorded. Blood pressure and heart rate are to be measured in the following order: supine, sitting, and standing after the subject has been in each position at least 3 minutes. Vital signs are to be completed before any blood is drawn.
- WOCBP will be given a urine pregnancy test. Any positive result must be confirmed by a serum pregnancy test. WOCBP with a positive serum pregnancy test result must discontinue the IMP and be withdrawn from the trial.
- Drug accountability will be performed for brexpiprazole and ADT.
- The investigator will adjust the dose of brexpiprazole as necessary within the range of 0.5 to 3 mg daily as described in [Section 3.2](#). If necessary, the dose of ADT can also be adjusted (see [Section 3.2.2.2](#)). Trial personnel will call the IVRS or access the IWRS to register the visit, to enter dose details for brexpiprazole and ADT, and to obtain blister card and bottle number assignments. The assigned open-label brexpiprazole and ADT will be dispensed to the subject.
- AEs and concomitant medications will be recorded.

3.6.1.8 End of Treatment (Week 26/ET)

The Week 26 visit signifies the end of treatment. Therefore, all subjects will undergo a complete evaluation at Week 26 (\pm 2 days). In addition, Week 26 evaluations are to be completed, if possible, for any subject withdrawn from the trial prematurely. Since the original 52 week open-label trial design has been modified as a part of Amendment 3 to shorten the duration of the trial to 26 weeks, ongoing subjects who have not reached their Week 26 visit will be re-consented and will follow Amendment 3 schedule of assessments. Ongoing subjects who have already completed their Week 26 visit at the time Amendment 3 is approved will follow Amendment 3 week 26/ET schedule of assessments at their next scheduled visit. The following activities and assessments will occur at Week 26 (or at the ET visit, if applicable):

- The investigator (or qualified designee) will administer the CGI-S and CGI-I.

- An adequately trained and experienced clinician will administer the SAS, AIMS, and BARS to assess EPS.
- The investigator (or qualified designee) will complete the “Since Last Visit” C-SSRS form.
- The subject will complete the MSFQ, SDS, IDS-SR, and the Follow-up RUF.
- A complete physical examination (including waist circumference) will be performed.
- Vital sign measurements (body weight, body temperature, blood pressure, and heart rate) will be recorded. Blood pressure and heart rate are to be measured in the following order: supine, sitting, and standing after the subject has been in each position at least 3 minutes. Vital signs are to be completed before any blood is drawn.
- A standard 12-lead ECG will be performed after the subject has been supine and at rest for at least 5 minutes. The ECG is to be completed before any blood is drawn.
- A fasting blood draw will be collected for clinical laboratory tests (hematology, including PT, aPTT, and INR; and serum chemistry, including prolactin, HbA1c, and TSH, with reflex to free T₄ if TSH is abnormal). Vital sign and ECG assessments should be completed before any blood samples are collected.
- Samples will be obtained for blood alcohol testing.
- Urine will be collected for urinalysis and urine screen(s) for drugs of abuse.
- WOCBP will be given a urine pregnancy test. Any positive result must be confirmed by a serum pregnancy test.
- Final drug accountability will be performed.
- Trial personnel will call the IVRS or access the IWRS to register completion or discontinuation from the trial.
- AEs and concomitant medications will be recorded.

3.6.1.9 Follow-up

Follow-up safety information (AEs and concomitant medications) will be collected 30 (+ 2) days after the last dose of open-label medication for all subjects (completers and early withdrawals). Follow-up information can be obtained via telephone contact or clinic visit at the investigator’s discretion.

3.6.2 Safety Assessments

3.6.2.1 Clinical Laboratory Tests

As it is unlikely that the final laboratory test results from the last scheduled visit of the prior double-blind phase 3 trial will be available at the time of enrollment in Trial 331-10-238, the investigator is to review the subject’s most recent laboratory test results from the prior double-blind phase 3 trial for compliance with the exclusion criteria

and the presence of abnormal laboratory test results that, in the investigator's judgment, are medically significant and would impact the safety of the subject or the interpretation of the trial results. Subjects meeting any of these criteria will be excluded from Trial 331-10-238. [Appendix 4](#) is included to assist investigators in their assessments of results that may be potentially medically significant, depending on the subject's medical history and clinical presentation. If one or more results from the screening/baseline sample are clinically significant and/or exclusionary when the results from the last scheduled visit of the prior double-blind phase 3 trial become available, the test(s) should be repeated. The subject may continue to receive trial medication pending results of the repeat laboratory tests at the investigator's discretion. If the abnormality remains upon retest, the medical monitor should be contacted to discuss the subject's eligibility for continued participation in Trial 331-10-238.

A central laboratory designated by the sponsor will be used for all laboratory testing required during the trial. The central laboratory should be used for all laboratory testing whenever possible (including unscheduled and follow-up labs, if needed). In cases where an immediate result is required for a particular laboratory test, the sample should be divided and sent to both a local laboratory and the designated central laboratory. Urine will be collected and blood will be drawn from subjects at the scheduled visits designated in Table 3.6-1. Additional urine and blood samples may be collected for further evaluation of safety as warranted by the investigator's judgment. Screening/baseline laboratory assessments will be performed after a minimum 8-hour fast per the protocol instructions for the double-blind phase 3 trials. All subjects must be fasting for a minimum of 8 hours prior to the blood draw at Week 26/ET and should be fasting for a minimum of 8 hours prior to all other blood draws during the Treatment Phase, if possible. If a subject is not fasting at a visit other than Week 26/ ET, the blood draw should still be performed and the status documented as nonfasting on the laboratory requisition sheet. The Week 26/ET blood draw must be rescheduled to accommodate the fasting requirement. Reports from the central laboratory should be filed with the source documents for each subject. The central laboratory will provide laboratory results to the sponsor electronically.

Table 3.6.2.1-1 Safety Clinical Laboratory Tests

Hematology:	Serum Chemistry:
WBC count with differential	ALP
RBC count	ALT or SGPT
Hematocrit	AST or SGOT
Hemoglobin	BUN
Platelet count	CPK
	Creatinine
Urinalysis:	LDH
pH	Total bilirubin
Specific gravity	Triglycerides
Protein	Cholesterol (total, LDL, and HDL)
Ketones	Calcium
Glucose	Chloride
Blood	Glucose
Microscopic exam (performed only if any part of the urinalysis is not negative)	Insulin
	Magnesium
	Bicarbonate
Urine Drug Screens:	Inorganic phosphorous
Amphetamines	Sodium
Barbiturates	Potassium
Benzodiazepines	Total protein
Cannabinoids	Uric acid
Cocaine	GGT
Marijuana	Prolactin
Methadone	Albumin
Opiates	
Phencyclidine	Additional Tests:
Propoxyphene	Urine pregnancy (WOCBP) ^a
	TSH, with reflex to free T ₄ if TSH is abnormal
Other:	PT, aPTT, and INR
Blood alcohol	HbA1c

ALP = alkaline phosphatase; ALT or SGPT = alanine transaminase; AST or SGOT = aspartate transaminase; BUN = blood urea nitrogen; CPK = creatine phosphokinase; GGT = gamma glutamyl transferase; HbA1c = glycosylated hemoglobin; HDL = high density lipoprotein; LDH = lactic dehydrogenase; LDL = low density lipoprotein; RBC = red blood cell.

^aAll positive urine pregnancy test results must be confirmed by a serum test. Subjects with a positive serum pregnancy test result at Screening/Baseline must not be enrolled and subjects with a positive serum pregnancy test result during the trial must discontinue treatment and be withdrawn from the trial.

Any value outside the normal range will be flagged for the attention of the investigator who must indicate whether or not a flagged value is of clinical significance. If one or more values are questionable, the test(s) may be repeated. Follow-up unscheduled labs should be performed on clinically significant abnormalities. Unscheduled laboratory tests may be repeated at any time at the discretion of the investigator for appropriate medical care.

To be eligible for Trial 331-10-238, subjects are not permitted to have laboratory values within the following exclusionary ranges:

- 1) Platelets \leq 75,000/mm³
- 2) Hemoglobin \leq 9 g/dL
- 3) Neutrophils, absolute \leq 1000/mm³
- 4) Aspartate transaminase (AST) $> 2 \times$ upper limit of normal (ULN)
- 5) Alanine transaminase (ALT) $> 2 \times$ ULN
- 6) Creatine phosphokinase (CPK) $> 3 \times$ ULN, unless discussed with and approved by the medical monitor
- 7) Creatinine \geq 2 mg/dL
- 8) HbA1c \geq 7.0%
- 9) Abnormal free T₄, unless discussed with and approved by the medical monitor.

(Note: Free T₄ is measured only if result for TSH is abnormal.)

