3.7.3 Individual Subject

If a subject discontinues from the trial prematurely, the reason must be fully evaluated and recorded appropriately in source documents and the eCRF. If the subject is being withdrawn because of an AE, that AE should be indicated as the reason for withdrawal. All subjects have the right to withdraw at any point during treatment without prejudice. The investigator can discontinue a subject's participation in the trial at any time if

medically necessary. In addition, subjects meeting the following criteria must be withdrawn from the trial:

- a) occurrence of any AE, intercurrent illness or abnormality in a laboratory assessment which, in the opinion of the investigator, warrants the subject's permanent withdrawal from the trial;
- b) treatment with a prohibited concomitant medication other than the use of appropriate medications for the treatment of AEs under direction of the investigator;
- c) subject noncompliance, defined as refusal or inability to adhere to the trial schedule or procedures (see [Section 3.11](#), Subject Compliance);
- d) at the request of the subject, investigator, sponsor or designee, or regulatory authority;
- e) subject becomes pregnant;
- f) subject cannot tolerate the minimum dose of brexpiprazole (ie, 0.5 mg/day), the minimum protocol-defined therapeutic dose of ADT (see [Table 3.2.1.2-1](#)), or requires a different ADT; or
- g) subject is lost to follow-up.

The investigator will notify the sponsor promptly when a subject is withdrawn. Subjects withdrawn prior to Week 26 must complete the Week 26/ET evaluations at the time of withdrawal. In addition, all subjects who withdraw prematurely from the trial will be assessed 30 (+ 2) days after the last dose of IMP for evaluation of safety. This assessment can be accomplished via telephone contact or clinic visit at the investigator's discretion. Withdrawn subjects will not be replaced.

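### The Week 26/ET blood draw has no nonfasting fallback, so an unfasted early stopper who does not return can lack any scheduled post-baseline blood panel

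*Protocol*

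**What the plan says.** Protocol Section 3.6.2.1 sets two rules for a subject who arrives unfasted. At any treatment visit other than Week 26/ET, "the blood draw should still be performed and the status documented as nonfasting on the laboratory requisition sheet". At Week 26/ET the rule reverses: "The Week 26/ET blood draw must be rescheduled to accommodate the fasting requirement". Footnote k of Table 3.6-1 agrees, saying of the laboratory tests that they "must be drawn after a minimum 8-hour fast at Week 26/ET". Neither place gives a window for the rescheduled draw or asks for a sample in the meantime.

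Two sections govern when a withdrawing subject has these evaluations. Section 3.7.3: "Subjects withdrawn prior to Week 26 must complete the Week 26/ET evaluations at the time of withdrawal". Section 3.6.1.8 is softer: "Week 26 evaluations are to be completed, if possible, for any subject withdrawn from the trial prematurely".

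The row "Clinical laboratory tests" in Table 3.6-1 is marked at Screening/Baseline, Week 14 and Week 26/ET only, and HbA1c follows the same pattern. The 30-day follow-up (Section 3.6.1.9) collects AEs and concomitant medications and may be done by telephone.

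**The concern.** The strict rule sits on the visit least able to bear it. Early termination can be unplanned, so the subject may well not be fasting, and someone leaving the trial has little reason to come back. For anyone who stops before Week 14, that draw is the only scheduled blood panel after baseline.

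The primary objective is safety and tolerability. A subject with no post-baseline panel contributes nothing to the laboratory change-from-baseline and incidence tables in SAP Section 9.2, or to the liver table in Section 9.2.1. The missing subjects are not a random subset: they are early stoppers, including those stopping because of an AE or a laboratory abnormality. Those who do return are sampled after dosing has ended, so the value may not reflect on-treatment exposure.

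**Working it through.** The plan states no figure to reproduce. The check sets the provisions side by side, then adds one exposure calculation.

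**1. Which subjects are affected under the current 26-week schedule** (Table 3.6-1)

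- Week 14 is Day 14 × 7 = 98 and Week 26 is Day 26 × 7 = 182, so 98/182 = 54% of the treatment period passes before the first scheduled on-treatment panel.
- Stops before Week 14, unfasted at ET, does not return: no scheduled post-baseline blood panel.
- Stops after Week 14, unfasted at ET, does not return: Week 14 panel kept, end-of-treatment panel lost.
- Unfasted at Week 26/ET and returns: panel obtained, but after the last dose. Table 3.6-1 shows no dispensing at Week 26/ET, and Section 3.6.1.8 places final drug accountability there.

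**2. Whether anything mandatory closes the gap**

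- The 30-day follow-up does not, because it has no laboratory component.
- Section 3.6.2.1 permits additional samples on the investigator's judgment and unscheduled tests for medical care. These are allowed, not required.

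**3. Whether the rule is wider than its purpose**

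In Protocol Appendix 4 and SAP Appendix 2, only glucose, total cholesterol, LDL, HDL and triglycerides have fasting-specific criteria. Glucose also has a nonfasting criterion (≥ 200 mg/dL, against ≥ 100 mg/dL fasting). AST, ALT, bilirubin, CPK, neutrophils, platelets and prolactin carry no fasting condition, yet are deferred with the rest.

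**4. Exposure at a rescheduled draw**

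Fraction remaining d days after the last dose = 2^(−24d / half-life in hours). Half-lives are from Protocol Section 1.2.1: 95.4 h is the steady-state mean in subjects with schizophrenia or schizoaffective disorder on 1 to 12 mg/day; 48.3 h is the low end of the single-dose range in healthy subjects.

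| Days after last dose | 95.4 h | 48.3 h |
|---|---|---|
| 1 | 84% | 71% |
| 2 | 71% | 50% |
| 3 | 59% | 36% |
| 7 | 30% | 9% |
| 14 | 9% | 1% |

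For example, 2^(−24/95.4) = 0.84 and 2^(−168/95.4) = 0.30. A delay of a day or two is off dosing but not off exposure; at a week or more, most of the drug has gone.

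**5. How the SAP treats such values**

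SAP Section 11.1 excludes evaluations more than seven days after the last dose, but applies its windowing convention to the listed efficacy and safety scales. Laboratory tests are not listed, so the handling of a late laboratory sample is unspecified.

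**The case against.** The rule has a sound purpose. Baseline is drawn fasting, weight gain was a known signal (Protocol Section 1.3), lipid criteria exist only for fasting samples, and the SAP tabulates treatment-emergent changes in lipids, glucose and metabolic syndrome. A fasting endpoint gives a like-for-like comparison. That stands, and it supports keeping the fasting draw for those tests. It does not support withholding the rest of the panel.

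Several stronger readings are tempting and are not supported:

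- *Early stoppers have no laboratory safety data.* Baseline values exist, only the blood draw is deferred (not the urine tests), and anyone stopping after Week 14 has that panel. Subjects followed under the superseded 52-week schedule (Appendix 16) also had panels at Weeks 1, 4 and 8.
- *An abnormality at an AE withdrawal will go unmeasured.* Investigators may sample at their discretion. This narrows the gap without closing it.
- *Returning subjects are sampled off drug.* That depends on a delay the protocol does not fix; nothing prevents a next-morning draw.
- *Section 3.7.3 is flatly contradicted.* The wording in Section 3.6.1.8 softens the clash, and the fasting rule can be read as specific to one component. The sections still need reconciling.
- *The number affected can be estimated.* Assuming that 20–40% of 3,000 stop early, 30–60% of those are unfasted and 20–50% of those do not return gives 3,000 × 0.20 × 0.30 × 0.20 = 36 up to 3,000 × 0.40 × 0.60 × 0.50 = 360 without an end-of-treatment panel. All three rates are assumed, none is in the documents, and the base includes subjects on the 52-week schedule. The tenfold range shows only that the number is unknown.

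**Conclusion.** The point holds in a limited form. Under the current 26-week schedule, the whole Week 26/ET draw must be deferred for an unfasted subject, with no fallback and no time limit. One who stops before Week 14 and does not return has no scheduled post-baseline blood panel; a later stopper loses the end-of-treatment panel. Subjects who return are sampled after the last dose, with about 84% of drug remaining at 1 day and 30% at 7 days. Those percentages assume that the 95.4-hour half-life, measured in a different patient population, applies here.

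The loss is selective for early stoppers and bears on the primary objective, but its frequency cannot be derived from the documents. The gap follows from the text without any assumed rate. This is a cheap improvement, not a flaw that invalidates the safety analysis.

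**What to change.** In Protocol Section 3.6.2.1, replace the rescheduling sentence with: *If a subject is not fasting at Week 26/ET, draw the full panel at that visit and document it as nonfasting; reschedule only the tests interpreted in the fasting state (glucose, lipids and, if wanted, insulin).* Align footnote k of Table 3.6-1. Reconcile Sections 3.6.1.8, 3.6.2.1 and 3.7.3 on when early termination evaluations are due, allowing for the fasting tests that may still follow later.

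In the SAP:

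- Use the at-visit sample for all tests that do not depend on fasting.
- Apply the existing nonfasting glucose criterion to unfasted glucose.
- Exclude unfasted lipids from the fasting criteria.
- State how laboratory values taken after the last dose are handled.

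The cost is a few sentences and a second small blood sample for subjects who return. The change extends the protocol's own practice at other visits, and Section 3.6.1.8 already plans a blood alcohol sample at this one.
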